7.7.1.3. Disallowed Concomitant Therapy

The use of disallowed concomitant therapies will lead to study treatment discontinuation as described in Section 8, at the discretion of the Investigator and/or Medical Monitor. Prior to the initiation of [REDACTED] the Medical Monitor and/or Sponsor should be consulted. Participants must refrain from the following disallowed concomitant therapies during study participation:

- Use of some compounds that may affect metabolism of BIIB122 (see Section 3.2.3 for a description of the important potential DDI effects), including but not limited to:
 - [REDACTED]
 - [REDACTED]
 - [REDACTED]
 - [REDACTED]
 - [REDACTED]
 - [REDACTED]
- Use of *Mucuna pruriens*, GLP-1 agonists, typical or atypical antipsychotics, cinnarizine, metoclopramide, tetrabenazine, reserpine and alpha methyldopa.
- For participants who are receiving LPs: Any antiplatelet medication (e.g., aspirin > 100 mg daily, clopidogrel, or NSAIDs) or any anticoagulant medication (warfarin, heparinoids, and direct coagulation factor inhibitors, e.g., apixaban, dabigatran, rivaroxaban) is prohibited from 7 days before to 48 hours after [REDACTED].
- Any investigational drug.

Medically indicated medication or treatment should not be withheld.

Further guidance on allowed and disallowed concomitant medications will be provided by the study's Medical Monitor on a case-by-case basis.

CONFIDENTIAL

The information contained herein may not be used, disclosed, or published without the written consent of Biogen MA Inc.

7.7.2. Cautionary Concomitant Substances

- Caution should be exercised for study participants who take [REDACTED] substrate drugs. Participants should be monitored for changes in tolerability or efficacy of this drug class. Participants are recommended to stagger [REDACTED] drugs and study treatment by at least 8 hours.

A partial list of [REDACTED] can be found in [REDACTED]

- Caution should be exercised for study participants who take sensitive [REDACTED] drugs with a narrow therapeutic index. Participants should be monitored for changes in tolerability or efficacy of this drug class.

A partial list of drugs in this class can be found in [REDACTED]

- Participants should refrain from excessive use of alcohol during the study; no more than 2 units of alcohol at a given time, or > 14 units per week for males and > 7 units per week for females. One unit of alcohol equals 12 oz (360 mL) beer, 1½ oz (45 mL) liquor, or 5 oz (150 mL) wine.

7.7.3. Concomitant Procedures

A concomitant procedure is any therapeutic intervention (e.g., surgery/biopsy, physical therapy) or diagnostic assessment (e.g., blood gas measurement, bacterial cultures) performed from the time of participant screening to the SFU and any UVs.

7.8. Continuation of Treatment after Study Completion

No further provisions are made for access to the study treatment after the study. If study treatment is proven to be beneficial, all regulatory requirements regarding poststudy access will be met.

CONFIDENTIAL

The information contained herein may not be used, disclosed, or published without the written consent of
Biogen MA Inc.

8. DISCONTINUATION OF STUDY TREATMENT AND WITHDRAWAL OF PARTICIPANTS FROM THE STUDY

8.1. Discontinuation of Study Treatment

Study treatment interruption is discussed in Section [7.2](#).

The use of disallowed concomitant therapies, described in Section [7.7.1.3](#), will lead to study treatment discontinuation, at the discretion of the Investigator and/or Medical Monitor.

A participant *must* permanently discontinue study treatment for any of the following reasons:

- The participant becomes pregnant. Study treatment must be discontinued immediately. Report the pregnancy according to the instructions in Section [11.4.1](#).
- The participant withdraws consent to continue study treatment.
- The participant experiences an AE that necessitates permanent discontinuation of study treatment.
- The participant experiences a medical emergency that necessitates unblinding of the participant's treatment assignment.
- The participant requires use of [REDACTED] or requires prolonged (≥ 1 month) use of [REDACTED]
- At the discretion of the Investigator for medical reasons.

The primary reason for discontinuation of study treatment must be recorded in the participant's eCRF.

The ET Visit will occur if a participant withdraws from the study.

If a participant discontinues study treatment but remains in the study, the EOT Visit will occur at the next scheduled visit. Participants who permanently discontinue study treatment early will be encouraged to continue study participation, maintaining the same schedule of study assessments as participants continuing in the double-blind treatment period.

8.2. Lost to Follow-Up

Participants will be considered lost to follow-up if they repeatedly fail to return for scheduled visits and are unable to be contacted by the study site.

The following actions must be taken if a participant fails to return to the study site for a required study visit:

CONFIDENTIAL

The information contained herein may not be used, disclosed, or published without the written consent of Biogen MA Inc.

- The site must attempt to contact the participant and reschedule the missed visit as soon as possible and counsel the participant on the importance of maintaining the assigned visit schedule and ascertain whether the participant wishes to and/or should continue in the study.
- In cases in which the participant is deemed lost to follow-up, the Investigator or designee must make every effort to regain contact with the participant. These contact attempts should be documented in the participant's medical record.
- Should the participant continue to be unreachable, that participant will be considered to have withdrawn from the study with a primary reason of lost to follow-up.

8.3. Withdrawal of Participants From the Study

Participants must be withdrawn from the study for any one of the following reasons:

- The participant withdraws consent for participation in the study.
- The participant enrolls into another interventional clinical study in which an investigational treatment or approved therapy for investigational use is administered.
- The participant is unwilling or unable to comply with the protocol.

The primary reason for the participant's withdrawal from the study must be recorded in the participant's eCRF.

Participants who withdraw from the study should undergo an ET Visit unless withdrawal is due to death or withdrawal of consent. Final follow-up visit assessments will be performed at the ET Visit. If an ET Visit cannot be performed, every effort must be made by the study site to contact the participant (e.g., by phone) to collect safety follow-up assessments remotely and the reason for discontinuation. The measures taken to follow-up must be documented.

Participants who withdraw from the study, for reasons other than a safety or tolerability event, may be replaced at discretion of the Sponsor.

CONFIDENTIAL

The information contained herein may not be used, disclosed, or published without the written consent of
Biogen MA Inc.

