5.2. Study Duration for Participants

The total study duration for each participant (including the Screening period) will be a minimum of approximately 103 weeks and a maximum of approximately 187 weeks as follows:

- [REDACTED] Screening period [REDACTED]
 - [REDACTED] minimum to [REDACTED] maximum (when the total number of events for the primary endpoint reaches approximately [REDACTED] events) double-blind, placebo-controlled treatment period
 - [REDACTED] SFU period
- [REDACTED]
[REDACTED]
[REDACTED]

The study duration for each participant depends on the time point at which he or she enters the study and will be after both the last participant completes SFU (Week [REDACTED] + [REDACTED] weeks or [REDACTED] weeks after the last dose in case of early termination) and the minimum target number of primary endpoint events has been reached. Based on timing of last participant in and rate of primary endpoint events, sites will be contacted to schedule EOT and SFU for enrolled participants.

The EOT/ET Visit is a visit where assessments are performed for participants who either discontinue study treatment early or withdraw from the study. The EOT Visit is scheduled to align with a participant's last dose. If a participant discontinues study treatment but remains in the study, the EOT Visit will occur at the next scheduled visit. Participants who permanently discontinue study treatment early will be encouraged to continue study participation, maintaining the same schedule of study assessments as participants continuing in the double-blind treatment period. The ET Visit will occur if a participant withdraws from the study.

CONFIDENTIAL

The information contained herein may not be used, disclosed, or published without the written consent of Biogen MA Inc.

The end of study date for a participant may be the last study visit, last follow-up telephone conversation, or last protocol-specified assessment, or if the participant has ongoing AEs that are being followed, the date may be the date of AE resolution.

See [Figure 1](#) for a schematic of the study design.

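### The Section 8.3 non-compliance bullet is not limited to people who can no longer be assessed; applied literally, it would end MDS-UPDRS follow-up in consenting, assessable participants

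*Combined protocol and SAP*

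**What the plan says.** The list in Section 8.3 (Withdrawal of Participants From the Study) opens: "Participants must be withdrawn from the study for any one of the following reasons". The three reasons are withdrawal of consent, enrolment in another interventional study, and this: "The participant is unwilling or unable to comply with the protocol". One reason is enough, and the third has no qualifier.

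The same section then says: "Final follow-up visit assessments will be performed at the ET Visit". If no ET Visit can be held, the site tries to collect safety information and the reason for discontinuation remotely. No later efficacy visit is described. Participants who withdraw "for reasons other than a safety or tolerability event, may be replaced at discretion of the Sponsor".

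Other sections deal with the usual forms of non-compliance differently:

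- Section 7.7.1.3: use of a disallowed therapy "will lead to study treatment discontinuation as described in Section 8, at the discretion of the Investigator and/or Medical Monitor". The consequence is for treatment, not for study participation, and it is discretionary.
- Section 8.1: "Participants who permanently discontinue study treatment early will be encouraged to continue study participation, maintaining the same schedule of study assessments". Section 5.2 repeats this, with such participants "maintaining the same schedule of study assessments as participants continuing in the double-blind treatment period".
- Section 8.2: after a missed visit the site reschedules, counsels, and is told to "ascertain whether the participant wishes to and/or should continue in the study".

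**The concern.** Stopping study treatment and leaving the study are different events, and the protocol mostly keeps them apart. The non-compliance bullet blurs the line. It is mandatory, and it refers to the protocol as a whole rather than to the visits or ratings. It also applies to people who still consent, because withdrawn consent has its own bullet.

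Consider a participant who attends every visit and accepts every MDS-UPDRS rating, but takes a disallowed medicine or persistently fails to take tablets as specified. Sections 7.7.1.3 and 8.1 leave room for that person to remain under assessment. The bullet, taken at its word, requires withdrawal. With about 55 sites planned, sites could reasonably differ in how they read it.

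At stake are outcomes that could have been collected. A participant withdrawn this way has been randomized and dosed and so stays in the full analysis set (Section 12.2), but has no scheduled ratings after the ET Visit. Replacement can restore the number of participants but not the missing outcomes of those already randomized. Treatment lasts 96 to 180 weeks in a progressive disease, so non-compliance might be related to progression. The documents do not show that it is.

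**Working it through.** The plan states no figure on this point, so the check is a comparison of texts.

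**Step 1: does the bullet force withdrawal?** Yes, as written. Section 8.3 uses mandatory wording, any single reason suffices, and the third reason mentions neither persistence, nor a counselling step, nor whether the person can still be rated.

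**Step 2: what follow-up remains?** Section 8.3 places the last assessments at the ET Visit. The MDS-UPDRS row of Table 1 appears to include that visit, although the table is hard to read in the public copy. One final rating is therefore likely if the visit takes place. If it does not, only remote safety contact and the reason are sought.

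**Step 3: does another section narrow the bullet?**

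| Situation | Section that addresses it | Outcome there | Outcome under the 8.3 bullet, read literally |
|---|---|---|---|
| Disallowed therapy | 7.7.1.3 | Treatment discontinuation, discretionary | Study withdrawal, mandatory |
| Treatment stopped early | 5.2, 8.1 | Encouraged to stay on the same assessment schedule | Study withdrawal, if the cause is non-compliance |
| Missed visit | 8.2 | Reschedule, counsel, find out whether to continue | Study withdrawal, if classed as unable or unwilling to comply |
| Missed dose | 7.1, 7.6 | Missed-dose instructions; compliance monitored and recorded | Study withdrawal, if classed as unable or unwilling to comply |

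The third column shows an intent to retain participants. None of these sections says that it limits or overrides the requirement in 8.3.

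**Step 4: which endpoints are exposed?**

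- *Change from Baseline to Week 96* in MDS-UPDRS Parts II and III combined, and in Parts I, II and III combined (Section 4). Both use a fixed time point, and the endpoint wording is not tied to the last dose. A participant withdrawn before Week 96 has no Week 96 score. How the analysis treats a missing score, or one obtained off treatment, is redacted in Section 12.3.2.
- *On-treatment assessments.* The bullet is not confined to people already off study drug. Someone still dosing when withdrawn also loses the later on-treatment visits that would otherwise have taken place.
- *Primary endpoint.* It runs over the treatment period (Section 12.3.1), which Table 1 footnote 10 ends at the participant's last dose. For someone already off drug, later scores may not count at all. The confirmation and censoring rules are redacted.

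**Step 5: can a size be given?** Not from the public text. It would need the number of participants withdrawn under this bullet who could still have been assessed, the planned dropout rate, the design hazard ratio and the censoring rules. The documents give no figure for the first, and the other three are redacted. A loss of power calculated from these gaps would reflect only the assumed withdrawal rate. The Synopsis also ties the length of treatment to reaching about 200 events, so longer follow-up could recover some events within the 180-week maximum.

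**The case against.** The strongest reply is that nobody would apply the bullet literally. Read that way, one missed tablet would remove a participant, yet Section 7.1 gives missed-dose instructions and Section 7.6 only monitors and records compliance. In context the bullet looks like a residual clause for people who will not or cannot go on. Someone who stops treatment but keeps attending, as Sections 5.2 and 8.1 encourage, is arguably complying with the protocol. Those left under the bullet would be mainly people who cannot follow the assessment schedule, and the revised wording would withdraw many of them too.

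Much of this stands. The residual reading is plausible, and Section 8.3 does not strictly contradict Sections 5.2, 8.1 or 8.2. But the text does not state that reading, and the wording is mandatory. The revised text would also keep someone whom the current text does not clearly protect: a consenting participant who attends for ratings but breaks a dosing or concomitant-therapy requirement.

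A reader might infer more than the documents support:

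- *That follow-up will in fact stop for every non-compliant participant.* This depends on how sites read the bullet.
- *That the primary analysis loses power.* The censoring rules are redacted, the planned dropout rate may already cover these withdrawals, and events may be recovered through longer follow-up.
- *That the treatment comparison is biased or the type I error inflated.* This would need withdrawals linked to outcome in a way that differs by arm, and nothing in the documents shows that.

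**Conclusion.** The point holds in conditional form. Section 8.3 states an unqualified, mandatory rule. If it is applied literally, it creates avoidable missing outcome data among randomized, dosed participants who still consent and could still be rated. The exposure is most direct for the two Week 96 change endpoints and for on-treatment visits of participants still dosing. For the primary endpoint the effect cannot be determined and may be nil, so no numerical size is given.

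The conclusion rests on two things: the literal wording of the bullet, and the absence of any statement elsewhere that restricts it. If the sponsor intends a residual clause, the matter is one of wording only. It is a cheap improvement that could be made, not an error that undermines the design.

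**What to change.** Reword the third bullet of Section 8.3 so that it covers only participants who are unwilling or unable to undergo any further study assessments. Add one sentence: other non-compliant participants, whatever is decided about their study treatment, remain on the Section 8.1 assessment schedule unless they withdraw consent to follow-up, are lost to follow-up under Section 8.2, or enrol in another interventional study.

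The cost is one bullet and one sentence, with no new procedures and no change to any treatment decision. Sites would do slightly more follow-up, and some of the retained participants would have partial or missed visits.

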9. EFFICACY, [REDACTED]

ASSESSMENTS

See Section 1.3 for the timing of all assessments.

Refer to the Study Reference Guide for additional information.

Tests and evaluations affecting primary endpoints and/or analyses may need to be repeated if the original results are lost or damaged. In these cases, participants will be asked to return to the study site to have the evaluations repeated.

[REDACTED]

9.1. Clinical Efficacy Assessments

Participants taking PD medications (e.g., levodopa, dopamine agonists, MAO-B inhibitors, anticholinergics, amantadine) during the study should perform the MDS-UPDRS Part III and [REDACTED] in the OFF state (PD medication held for \geq 8 hours before the time of assessment) at in-clinic visits. [REDACTED]

The following clinical assessments will be performed to evaluate the efficacy of BIIB122. At the baseline visit, all efficacy assessments will be performed before BIIB122 dosing.

- MDS-UPDRS is a multimodal scale assessing impairment and disability, includes Parts I to IV.
 - Part I assesses nonmotor experiences of daily living, administered by the participant.
 - Part II assesses motor experiences of daily living that reflect the participant's subjective perception of their own condition, administered by the participant.
 - Part III assesses the motor signs of PD, administered by the rater/certified individual.
 - Part IV assesses motor complications of PD, administered by the participant.

[REDACTED]

- The mSE-ADL scale reflects the speed, ease, and independence with which an individual performs daily activities or personal chores.

CONFIDENTIAL

The information contained herein may not be used, disclosed, or published without the written consent of Biogen MA Inc.

Country	Percentage of population aged 65 and older in 2010
United States	13.4%
Canada	14.0%
United Kingdom	14.5%
Germany	14.8%
France	15.0%
Italy	15.2%
Spain	15.5%
Australia	15.8%
New Zealand	16.0%
Sweden	16.2%
Norway	16.5%
Iceland	16.8%

CONFIDENTIAL

The information contained herein may not be used, disclosed, or published without the written consent of Biogen MA Inc.

9.2. Laboratory Efficacy Assessments

Not applicable.

CONFIDENTIAL

The information contained herein may not be used, disclosed, or published without the written consent of Biogen MA Inc.

CONFIDENTIAL

CONFIDENTIAL

CONFIDENTIAL

The information contained herein may not be used, disclosed, or published without the written consent of
Biogen MA Inc.

10. SAFETY ASSESSMENTS

See Section 1.3 for the timing of all safety assessments.

10.1. Clinical Safety Assessments

The following clinical assessments will be performed to evaluate the safety profile of BIIB122. At the baseline visit, all safety assessments must be performed before BIIB122 dosing.

- AE and SAE recording
- Physical (including weight) and neurological examinations
- Vital sign measurements (temperature, HR, BP, and respiratory rate). Blood pressure will be measured after the participant has been resting in a seated position for at least 5 minutes. Orthostatic vital sign measurements will be obtained whenever blood pressure is read, in the following manner: after supine blood pressure and heart rate are measured, the participant should stand, and blood pressure and heart rate should be measured after standing 1 minute and again after 3 total minutes.
- 12-Lead ECGs
- C-SSRS
- Concomitant therapy and procedure recording
- PFTs
- Pulse oximetry

10.2. Laboratory Safety Assessments

Samples will be analyzed using Good Laboratory Practice-validated assays.

The following laboratory assessments will be performed to evaluate the safety profile of BIIB122. At the baseline visit, all safety assessments must be performed before BIIB122 dosing.

- Hematology: Complete blood count with differential and platelet count
- Serum chemistry: Electrolytes, total protein, albumin, creatinine, blood urea nitrogen, uric acid, bilirubin (total and direct), alkaline phosphatase, alanine aminotransferase, aspartate aminotransferase, gamma-glutamyl transferase, glucose, calcium, and phosphorus
- Coagulation: INR, PT, and APTT
- Urinalysis: Dipstick for blood, protein, and glucose (microscopic examination may also be performed) and urine ACR

CONFIDENTIAL

The information contained herein may not be used, disclosed, or published without the written consent of
Biogen MA Inc.

- Serum and/or urine pregnancy tests

10.3. Product-Specific Safety Assessments

Not applicable.

CONFIDENTIAL

The information contained herein may not be used, disclosed, or published without the written consent of
Biogen MA Inc.

11. SAFETY DEFINITIONS, RECORDING, REPORTING, AND RESPONSIBILITIES

Throughout the course of the study, every effort must be made to remain alert to possible AEs, device AEs, ADEs, and device deficiencies. If an AE, device AE, ADE, or device deficiency occurs, the first concern should be for the safety of the participant. If necessary, appropriate medical intervention should be provided.

At the signing of the ICF, each participant and/or his/her legally authorized representative, in accordance with local practice and regulations, must be given the names and telephone numbers of site staff for reporting SAEs, device SAEs, UADEs, reportable device deficiencies, pregnancies, overdoses, and medical emergencies. Throughout the protocol, the Sponsor is named, but reporting may be done through a CRO.

For the classification of [REDACTED], refer to the [REDACTED] Investigator's Brochure. Safety monitoring, recording, and reporting are described in the sections below.

